5.1.4 Stage I – Dose limiting toxicity definition and stopping rules

To determine the safety of pembrolizumab in combination with blinatumomab in patients with acute lymphoblastic leukemia, the combination will be administered to 3-6 patients with relapsed or refractory B-lineage acute lymphoblastic leukemia.

Toxicity will be graded according to the National Cancer Institute (NCI) Common Toxicity Criteria for Adverse Events (CTCAE) version 4.03. Adverse events will be assessed continuously throughout therapy.

Dose Limiting Toxicity (DLT) is defined as a clinically significant adverse event that is considered by the investigator to be probably or definitely related to pembrolizumab or the combination of pembrolizumab and blinatumomab occurring within 42 days of the first dose of pembrolizumab on Day 15 of Cycle 1 as follows:

- Any Grade 3-5 non-hematologic toxicity EXCEPT:
 - Grade 3 cytokine release syndrome that resolves in 7 days or less
 - Grade 3 neurotoxicity that resolves in 7 days or less
 - Grade 3 infections
 - Grade 3 or 4 febrile neutropenia unless deemed by investigator to be definitely related to pembrolizumab
 - Grade 3 or 4 laboratory abnormalities unless they warrant temporary discontinuation of pembrolizumab or permanent discontinuation of blinatumomab (see tables, 5.7.1 and 5.7.2)
 - Grade 3 or 4 lymphopenia
- Any clinically significant toxicity that precludes administration of the next scheduled dose for more than 14 days

Decision to proceed to Stage 2 of the study will be made as follows below.

Number of Patients with DLT	Decision Rule
0 out of 3	Proceed to Stage 2 of study.
1 out of 3	Enter at least 3 more patients. 
 If 0 of these 3 patients experience DLT, proceed to Stage 2 of study If 1 or more of this group suffer DLT, then study will be placed on hold. Decision regarding dosing of pembrolizumab and continuation of study will be made after discussion between sponsors and investigators.
≥ 2	Study will be placed on hold and the FDA notified. Decision regarding dosing of pembrolizumab and continuation of study will be made after discussion between sponsors, investigators and FDA.
≤ 1 out of 6	Proceed to Stage 2 of study.

Subjects withdrawing from investigational treatment during the DLT monitoring period for a reason that is definitely unrelated to toxicity of the study agent (e.g. disease progression, patient withdrawal of consent) will be replaced.

5.1.5 Stage 2 - Dose expansion

If Stage 1 of the study proves safe, 18-21 additional subjects for a total of 24 subjects will be enrolled to assess the primary endpoint. Subjects from both stages will be included in the efficacy analysis.

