10. STATISTICAL CONSIDERATIONS

10.1 Study Design/Study Endpoints

This is a Phase I/II single-arm, open-label, multicenter study of pembrolizumab in combination with blinatumomab. This study includes a Phase I safety run-in of 3-6 patients followed by accrual of 18-21 additional patients for a total of 24.

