10.5 Data Analyses Plans

10.5.1 Primary Analysis

Simon's 2-stage for efficacy

We plan a Simon's 2-stage MiniMax design evaluation of the combination of blinatumomab and pembrolizumab in relapsed or refractory B-cell ALL with >50% blasts in the marrow.

We assessed the sample size for studying using overall response rate (CR + CRh). From recent large Phase II study including 189 subjects with relapsed/refractory B-lineage ALL, ORR (CR + CRh) to blinatumomab monotherapy was approximately 29% in patients with >50% lymphoblasts in the bone marrow (Topp et al. 2015). Response rates for PD-1 inhibitors in relapsed or refractory ALL are unknown but given mechanism of action it likely approaches zero.

An absolute increase in the overall response rate of 25 percentage points (i.e. to 54% ORR in patients evaluable for efficacy) or greater will demonstrate sufficient activity to consider the regimen for further study.

To calculate sample sizes for Stage 1 and Stage 2 we used a probability of type I error (α) = 0.05 and a power ($1-\beta$) = 0.80 with $p_0=0.29$ and $p_1=0.54$.

The null hypothesis that the true response rate is 0.29 will be tested against a one-sided alternative. In the first stage, 18 patients evaluable for efficacy will be accrued. If there are 7 or fewer responses in these 18 patients, the study will be stopped. Otherwise, 6 additional patients will be accrued for a total of 24 patients evaluable for efficacy of the combination. The null hypothesis will be rejected if 11 or more responses are observed in 24 evaluable patients. This design yields a type I error rate of 0.05 and power of 0.80 when the true response rate is 0.54. The likelihood of early termination is 0.88, if the null hypothesis is true.

Safety rules

At the time of the Stage 1 efficacy analysis, all patients will be reviewed again for DLTs as defined in Section 5.1.4 occurring at any time during therapy.

A DLT rate exceeding 0.3 will be considered unacceptable. The first 3, 6, 12, and 24 patients will be monitored for DLTs. The first 6 patients will be monitored every other week. The next 6 patients will be monitored monthly. Subsequent patients will be monitored every other month.

k	1	2	3	4
n_k	3	3	6	12

N_k	3	6	12	24
r_k	1	1	3	5

Table: Monitoring design for DLTs. The stage is denoted by k . The number of patients accrued during and up to stage k are denoted by n_k and N_k respectively. The critical value at stage k is denoted by r_k .

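### Sections 5.1.5 and 10.1 take enrolment to 24 without the 18-patient futility stop that 10.5.1 requires, and Stage 1/Stage 2 has two meanings; the 11-of-24 boundary meets 0.05 only if that stop is binding.

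*Combined protocol and SAP*

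**What the plan says.** **The stopping rule.** Section 10.5.1 sets out the design: "We plan a Simon's 2-stage MiniMax design evaluation of the combination of blinatumomab and pembrolizumab". On the first stage it says "In the first stage, 18 patients evaluable for efficacy will be accrued", followed by "If there are 7 or fewer responses in these 18 patients, the study will be stopped". Otherwise 6 more patients are accrued, and the null hypothesis is rejected at 11 or more responses in 24. The plan states: "This design yields a type I error rate of 0.05 and power of 0.80 when the true response rate is 0.54". It puts the probability of early termination under the null at 0.88.

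**The enrolment rule.** Section 5.1.5 sets one condition, that Stage 1 proves safe; then "18-21 additional subjects for a total of 24 subjects will be enrolled to assess the primary endpoint". Section 10.1 describes a run-in of 3-6 patients "followed by accrual of 18-21 additional patients for a total of 24". Neither section mentions an efficacy look or refers to 10.5.1.

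**The labels.** In 5.1.1, 5.1.4, 5.1.5 and 10.4, Stage 1 is the safety run-in and Stage 2 the expansion. The decision table in 5.1.4 moves the trial to Stage 2 on DLT counts alone. In 10.5.1 the same labels mean the Simon stages, and its safety rules rely on that meaning: "At the time of the Stage 1 efficacy analysis, all patients will be reviewed again for DLTs".

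**The concern.** The stop at 18 appears in one subsection only. The treatment plan that sites work from, and the design summary that opens the statistics section, both go from the run-in to 24. The synopsis gives 24 subjects and a one-sided binomial method, with no mention of two stages.

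Three things are at stake. The rejection boundary was chosen together with the stop, so the type I error changes if the stop is not applied. The stop also keeps patients 19-24 off a regimen that the plan would by then have judged not worth pursuing. Finally, the DLT re-review is tied to a Stage 1 analysis, which falls after 3-6 patients under the Section 5 meaning and after 18 under the 10.5.1 meaning.

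**Working it through.** **Inputs, all from 10.5.1.** p0 = 0.29, one-sided; p1 = 0.54; n1 = 18; stop if X1 ≤ 7; n2 = 6; reject if X1 + X2 ≥ 11. X1 and X2 are independent binomial counts. Patients from the run-in count toward the 18, since 5.1.5 and 10.4 include them in the efficacy evaluation.

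**Step 1: reproduce the plan's figures, with the stop.**

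- Rejection probability = Σ over x = 8 to 18 of P(X1 = x) × P(X2 ≥ 11 − x).
- At p0 this is 0.0499 (stated 0.05). At p1 it is 0.801 (stated 0.80).
- Early termination under the null = P(X1 ≤ 7 | 18, 0.29) = 0.880 (stated 0.88).
- An exhaustive search returns this same design as the minimax solution.

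The stated figures are therefore right for the design in 10.5.1.

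**Step 2: remove the stop, keep 11 of 24.** Rejection probability = P(X ≥ 11 | 24, p), which is 0.0597 at p0 and 0.843 at p1.

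**Step 3: where the difference comes from.** It is the probability under the null of 7 or fewer responses in 18 followed by enough responses in the next 6 to reach 11.

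| X1 | P(X1) | X2 needed | P(X2) | Product |
|---|---|---|---|---|
| 5 | 0.2048 | 6 | 0.0006 | 0.0001 |
| 6 | 0.1812 | ≥ 5 | 0.0093 | 0.0017 |
| 7 | 0.1269 | ≥ 4 | 0.0628 | 0.0080 |

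The sum is 0.0098, which equals 0.0597 − 0.0499. Fewer than 5 responses in 18 cannot reach 11.

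**Step 4: could 24 patients without a stop be tested within 0.05?** Rejecting at 12 or more of 24 gives a type I error of 0.0242, but power falls to 0.726. So 11 of 24 satisfies 0.05 only with a binding stop, and a single look at 24 cannot meet both stated targets.

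**Step 5: patients treated under the null.** With the stop, expected N = 18 + 6 × (1 − 0.880) = 18.7. Without it, N = 24. Six more patients are treated in the 88% of null trials that would have stopped.

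**Step 6: does the 18 in 5.1.5 and 10.1 refer to the interim?** No. There, 18-21 is 24 less the run-in: 24 − 6 = 18 and 24 − 3 = 21. It shares a number with the first Simon stage only by coincidence, which makes misreading easier.

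**The case against.** A reader might infer that the plan has dropped the futility stop and that its 0.05 is wrong. The documents do not support either reading.

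- The stop is explicit in 10.5.1, which refers again to a Stage 1 efficacy analysis. Section 10.2 sends the reader to 10.5.1 for the accrual rationale. Sections 5.1.5 and 10.1 are silent on the look; they do not cancel it.
- Sections 5.1.1 and 10.4 give 21 further subjects as an upper limit, and the table in 10.3 is headed as maximum accrual. On that reading 24 is a ceiling.
- The stated error rates reproduce for the design as specified.
- A site cannot run on to 24 unaided. Under 6.1.4 and 11.5 the coordinating office must issue an ID and confirm eligibility before each patient starts treatment.
- The excess in type I error is about one percentage point, and power would rise in the same scenario.

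All of this stands, and it limits the point to one of consistency. It does not remove it. The upper limit of 21 is fully explained by the size of the run-in, so it does not signal a futility stop. Section 10.2 points to a rationale, not to a condition on enrolment. The only condition that 5.1.5 does state is safety, so a coordinating office consulting that section finds no reason to hold after patient 18.

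**Conclusion.** The point holds as a conflict between the enrolment wording in 5.1.5 and 10.1 and the stopping rule in 10.5.1, made worse by labels with two meanings. The design is sound and its stated operating characteristics are correct.

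The consequences are conditional: they arise only if 5.1.5 and 10.1 are followed in place of 10.5.1 while 11 of 24 is kept. Type I error would then be 0.0597 instead of 0.0499, power 0.843 instead of 0.801, and N 24 instead of an expected 18.7 under the null. For patients, the extra six treated in 88% of null trials matter more than the 0.0098 of type I error.

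The figures assume independent responses, a null rate of exactly 0.29, and that the 18 and 24 are efficacy-evaluable patients as 10.5.1 requires.

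**What to change.** - In 5.1.5 and 10.1, write up to 24. State that enrolment beyond 18 efficacy-evaluable patients, run-in included, proceeds only if 8 or more have responded, as 10.5.1 specifies.
- In 5.1.1 and 10.4, add a cross-reference to that rule.
- Call the 3-6 patient part the safety lead-in throughout, including the decision table in 5.1.4, and keep Stage 1 and Stage 2 for the Simon stages. This also fixes the timing of the DLT re-review in 10.5.1.
- State that accrual is held until the rule can be applied to the first 18.

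Sample size, boundaries and treatment do not change. The cost is an amendment to wording plus the hold itself, which 10.5.1 already implies but does not spell out. The endpoint in 3.1.1 is response after 1 or 2 cycles, and the second-cycle marrow is due on Day 29 + 8 days of a second 42-day cycle. For the 18th patient that is study day 42 + 29 = 71 to 79, or 70 to 78 days after starting: roughly 10-11 weeks. The hold would be shorter if the eighth response is recorded sooner.

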5.1.6 Response assessment

Response will be assessed by bone marrow aspiration and biopsy on:

- Cycle 1, Day 12, 13, or 14
- Cycle 1, Day 29 + 8 days
- Cycle 2, Day 29 + 8 days
- Cycle 3, Day 29 + 8 days
- Cycle 4, Day 29 + 8 days
- Cycle 5, Day 38 + 8 days

Bone marrow aspiration and biopsy should occur at the time of any relapse or suspected relapse.

Bone marrow aspirates and biopsies should be sent for standard morphology, flow cytometry, karyotype, and *in situ* hybridization for any abnormalities documented on screening bone marrow studies.

Minimal residual disease testing on a first pull bone marrow aspirate should be sent overnight to University of Washington for analysis.

Requisition form is available in **Appendix C**.

For patients with extramedullary disease at diagnosis, repeat imaging using the same modality as at diagnosis is to be performed to assess response on:

- Cycle 1, Day 12, 13, or 14
- Cycle 1, Day 29 + 8 days
- Cycle 2, Day 29 + 8 days

Cycle 5, Day 38 + 8 days

Repeat imaging should occur at the time of any relapse or suspected relapse.

5.2 Pre-Medications

Pembrolizumab premedications:

No premedications are required although allowed at investigator discretion or institutional standard of care. Corticosteroids are not to be used as premedications in the absence of prior infusion-related toxicity. For prior infusion-related reactions, administration of premedications should occur per institutional standard of care.

Blinatumomab premedications:

Dexamethasone 20 mg IV once one hour (+/- 30 min) prior to start of blinatumomab infusion on Day 1 of each cycle and one hour (+/- 30 min) prior to any dose increase from 9 mcg/day to 28 mcg/day.

In addition, if blinatumomab infusion is interrupted for more than 4 hours, dexamethasone 20 mg IV once one hour (+/- 30 min) prior to restarting blinatumomab should be given.

Other non-corticosteroid premedications may be administered per institutional standard of care.

5.3 Concomitant therapy

5.3.1 CNS relapse prophylaxis

Intrathecal chemotherapy to prevent CNS relapse will be administered as follows:

Methotrexate 15 mg intrathecal or intraventricular at screening, Day 29 + 8 days of cycles 1-4, and Days 38 + 8 days of cycle 5 (end of treatment).

5.3.2 Infection prophylaxis

5.3.2.1 Viral prophylaxis

Viral prophylaxis will consist of **acyclovir** to prevent HSV and VZV reactivation. Dosing as follows:

Acyclovir 400 or 800 mg oral twice daily continuously until completion of study therapy or longer at discretion of investigator

For patients undergoing treatment or prophylaxis with alternate antiviral agents targeting HSV and VZV, acyclovir prophylaxis may be suspended until completion of alternate therapy.

5.3.2.2 *Pneumocystis jiroveci* prophylaxis

All study patients receiving study therapy must receive *Pneumocystis jiroveci* pneumonia (PJP) prophylaxis during active therapy per institutional standard of care. **Trimethoprim-sulfamethoxazole (TMP-SMX)** prophylaxis is recommended. Alternate PJP prophylaxis agents for patients intolerant of TMP-SMX include **dapsone, atovaquone, or pentamidine**.

5.3.2.3 Fungal prophylaxis

During periods of neutropenia patients should receive fungal prophylaxis. Recommended treatment is:

Fluconazole 400 mg oral daily for absolute neutrophil count <500/mcl

Alternate prophylactic regimens including no prophylaxis are allowed per local standard of care and investigator discretion.

5.3.2.4 Neutropenia prophylaxis

Prophylaxis during neutropenia including antibacterial and antifungal therapies is to be administered per local standard of care.

5.3.3 Other anti-leukemic therapies

No other anti-leukemic therapies outside of those described in this protocol are allowed.

5.3.4 Vaccines

Live vaccines within 30 days of treatment administration are prohibited.

5.3.5 Other concomitant medications

Medications required to treat adverse events, manage leukemia-related or treatment-related symptoms, maintain concurrent stable disease (e.g., controlled hypertension) as well as supportive care agents such as blood component transfusions, and pain medications are allowed per institutional standards of care and investigator discretion. The patient needs to notify the local investigational team about any new medications he/she takes after the start of the study medication. All medications other than study drug and significant non-drug therapies administered after the patient starts treatment with study drug must be recorded in the patient's medical record. Palliative and supportive care for disease-related symptoms, including pain medications, is permitted per local standards of care.

5.4 Prohibited concomitant therapy

Except as described in the protocol, **corticosteroids** are prohibited for any indication given the anti-leukemic activity of these agents interfering with interpretation of the study results.

Corticosteroids are permitted to prevent or treat infusion reactions and cytokine release syndrome or Events of Clinical Interest (ECI, See appendix G). Topical or inhaled steroids are

permitted.

Use of **G-CSF** or **GM-CSF** is prohibited.

Any other potentially anti-neoplastic therapy is prohibited regardless of indication for administration.

Any biologic, antibody, or immunomodulatory agent, except as described in the protocol, is prohibited.

Other investigational therapies must not be used while the patient is on the study. Anticancer therapy (chemotherapy, biologic or radiation therapy, and surgery) other than the study treatments must not be given to patients while the patient is on the study medication. If such agents are required for a patient then the patient must be removed from the study.

5.5 Diet/Activity/Other Considerations

5.5.1 Diet

Subjects should maintain a normal diet unless modifications are required to manage an AE such as diarrhea, nausea or vomiting. The use of alternative or complementary herbal or other dietary modifications should be discouraged.

5.5.2 Contraception

Pembrolizumab and blinatumomab may have adverse effects on a fetus *in utero*. Furthermore, it is not known if pembrolizumab or blinatumomab has transient adverse effects on the composition of sperm. Non-pregnant, non-breast-feeding women may be enrolled if they are willing to use 2 methods of birth control or are considered highly unlikely to conceive. Highly unlikely to conceive is defined as 1) surgically sterilized, or 2) postmenopausal (a woman who is ≥ 45 years of age and has not had menses for greater than 2 years will be considered postmenopausal), or 3) not heterosexually active for the duration of the study. The two birth control methods must be two barrier methods OR a barrier method plus a hormonal method to prevent pregnancy. Subjects should start using birth control from study Day 1 throughout the study period and for 120 days after the last dose of study therapy.

The following are considered adequate barrier methods of contraception: diaphragm, condom (by the partner), copper intrauterine device, sponge, or spermicide. Appropriate hormonal contraceptives will include any registered and marketed contraceptive agent that contains an estrogen and/or a progestational agent (including oral, subcutaneous, intrauterine, or intramuscular agents).

Subjects should be informed that taking the study medication may involve unknown risks to the fetus (unborn baby) if pregnancy were to occur during the study. In order to participate in the study they must adhere to the contraception requirement (described above) for the duration of the study and during the follow-up period defined in **Section 8.7-Reporting of Pregnancy and Lactation** to the Sponsor and to Merck and/or Amgen depending of exposure to pembrolizumab or blinatumomab or both. If there is any question that a subject will not reliably comply with the requirements for contraception, that subject should not be entered into the study.

5.5.3 Use in Pregnancy

If a subject inadvertently becomes pregnant while on treatment with pembrolizumab or blinatumomab, the subject will immediately be removed from the study. The site will contact the subject at least monthly and document the subject's status until the pregnancy has been completed or terminated. The outcome of the pregnancy will be reported to the Sponsor and to Merck and/or Amgen depending on exposure to pembrolizumab or blinatumomab, respectively, without delay and within 24 hours to the Sponsor and within 2 working days to Merck and/or Amgen if the outcome is a serious adverse experience (e.g., death, abortion, congenital anomaly, or other disabling or life-threatening complication to the mother or newborn).

The study investigator will make every effort to obtain permission to follow the outcome of the pregnancy and report the condition of the fetus or newborn to the Sponsor. If a male subject impregnates his female partner the study personnel at the site must be informed immediately and the pregnancy reported to the Sponsor and to Merck and/or Amgen and followed as described above and in **Section 8.7**.

5.5.4 Use in Nursing Women

It is unknown whether pembrolizumab or blinatumomab is excreted in human milk. Since many drugs are excreted in human milk, and because of the potential for serious adverse reactions in the nursing infant, subjects who are breast-feeding are not eligible for enrollment.

5.6 Supportive Care Guidelines

In addition to the supportive care measures outlined above, subjects should receive appropriate supportive care measures as deemed necessary by the treating investigator. Suggested supportive care measures for the management of adverse events with potential immunologic etiology are outlined below and in greater detail in the ECI guidance document. Where appropriate, these guidelines include the use of oral or intravenous treatment with corticosteroids as well as additional anti-inflammatory agents if symptoms do not improve with administration of corticosteroids. Note that several courses of steroid tapering may be necessary as symptoms may worsen when the steroid dose is decreased. For each disorder, attempts should be made to rule out other causes such as metastatic disease or bacterial or viral infection, which might require additional supportive care. The treatment guidelines are intended to be applied when the investigator determines the events to be related to pembrolizumab.

Note: if after the evaluation the event is determined not to be related, the investigator is instructed to follow the ECI reporting guidance but does not need to follow the treatment guidance (as outlined in the ECI guidance document). Refer to **Section 5.7** below for dose modification.

It may be necessary to perform conditional procedures such as bronchoscopy, endoscopy, or skin photography as part of evaluation of the event. Suggested conditional procedures, as appropriate, can be found in the ECI guidance document.

